## 9.2. Setting

The source population for this study will consist of all individuals with at least one medical or pharmacy claim from 11 September 2023 through 31 March 2024. The end date of 31 March 2024 was chosen based on the assumption that vaccine uptake will be similar to uptake during the 2022-2023 season. During the 2022-2023 COVID-19 season, the end of March reflected the time when uptake of the bivalent booster was no longer increasing (i.e., most individuals who received the bivalent booster dose had done so prior to March 2023), and COVID-19 cases declined substantially from their peak ([CDC, 2020](#)).

Trends in COVID-19 vaccine uptake will be monitored until 30 June 2024 using the Centers for Disease Control and Prevention's (CDC) Weekly COVID-19 Vaccination Dashboard ([CDC, 2023d](#)), which publishes estimates of the proportions of children aged 6 months through 17 years and adults 18 years and older who have received a COVID-19 vaccine each week during the 2023-2024 season. If in the final week of reported data for June 2024 these estimates show vaccine uptake in either children or adults that is 1% or greater than the respective estimates reported for the first week of April 2024 (i.e., an increasing trend in COVID-19 vaccine uptake from the first week of April 2024 to the last week of June 2024), then the Sponsor will extend the end date of the accrual period into October 2024, and the updated source population will be reflected in the final study report. This date reflects the latest accrual date that still allows for meeting of the current study milestones. This revision, if needed, will be communicated to the FDA as a protocol amendment.

Each study design will have its own inclusion and exclusion criteria, as listed below.

### 9.2.1. SCRI

#### 9.2.1.1. Inclusion Criteria

Patients must meet all of the following inclusion criteria to be eligible for inclusion in Phase 1 of the study:

1. Receive at least one dose of the COMIRNATY 2023-2024 Formula from the date of the COMIRNATY 2023-2024 product launch through 31 March 2024.
2. Age  $\geq$  6 months when receiving their first recorded dose of the COMIRNATY 2023-2024 Formula.
3. Have continuous medical and pharmacy insurance coverage in the 365 days prior to their vaccination date (as defined in [Section 9.2.3](#)), or since birth if the vaccination occurred at  $<$  1 year of age.
4. Experience a safety outcome of interest during a risk interval or control period (on or after vaccination, as defined in [Section 9.3.2](#)).
5. Do not experience the safety outcome of interest during the clean period (prior to vaccination, as defined in [Section 9.3.2](#)).

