**Population:** The source population for this study will consist of all individuals with at least one medical or pharmacy claim from 11 September 2023 through 31 March 2024. In Phase 1, individuals age  $\geq 6$  months will be eligible for inclusion if they receive at least one dose of the COMIRNATY 2023-2024 Formula from the date of product launch through 31 March 2024, have continuous medical and pharmacy insurance coverage in the 365 days prior to their vaccination date, experience a safety outcome of interest during a risk or control period, and do not experience the safety event of interest during the clean period prior to vaccination. In Phase 2, individuals age  $\geq 6$  months will be eligible for inclusion in the exposed cohort if they receive a dose of the COMIRNATY 2023-2024 Formula and have continuous medical and pharmacy insurance coverage in the 365 days prior to their vaccination. Individuals age  $\geq 6$  months will be eligible for inclusion in the unexposed cohort if they do not receive a dose of the COMIRNATY 2023-2024 Formula but do have a healthcare encounter and if they have continuous medical and pharmacy insurance coverage in the 365 days prior to their healthcare encounter. Individuals in the unexposed cohort will be matched to those in the exposed cohort if their healthcare encounter is in the same 14-day calendar period as the exposed individual's vaccination date and if they are in the same age group.

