#### **8.1.1. Primary Objective:**

- To estimate the incidence of pre-specified safety events of interest following vaccination with the COMIRNATY 2023-2024 Formula compared to the incidence of these events during a control window (i.e., expected rates of these events).

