#### 9.1.1. SCRI

Phase 1 will monitor the incidence rate of pre-specified safety events of interest in a general population of individuals who receive the COMIRNATY 2023-2024 Formula using an SCRI study design that tracks post-vaccination risk intervals and control (reference) periods for each vaccinated individual. Monitoring will be conducted during a pre-specified risk period immediately following vaccination, and the observed rate of events during this risk period will be compared to that of a control period temporally removed from the vaccination event. As depicted in [Figure 1](#), only individuals who receive the COMIRNATY 2023-2024 Formula will be included in the SCRI study ([Baker et al., 2015](#)). Within each individual, outcomes occurring during the risk interval will be compared with those occurring during the control period, in order to determine whether these outcomes occur more frequently immediately after vaccination as compared with a reference period. A washout period may be inserted between the risk interval and the control period to ensure that events relating to the vaccine are not incorrectly attributed to the control period. To ensure that observed outcomes are truly incident, a period free from the outcome of interest (clean period) may be required prior to vaccination.

090177e1a5be86fe\Approved\Approved On: 19-Mar-2026 15:57 (GMT)

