#### **9.6. Data Management**

All analyses will be conducted using Statistical Analysis System (SAS) version 9.4 (SAS Institute Inc., Cary, North Carolina) and SAS Enterprise Guide 6.1 or later. The data will be

---

 CPT copyright 2024 American Medical Association. All rights reserved.

extracted once per report. All reports will utilize the structured data only. The interim report will include summarized results from the Optum pre-adjudicated claims database described in [Section 9.4.1](#). The final report will include results summarized from the ORD as described in [Section 9.4.2](#). The characteristics of patients to be included in each data extract (e.g., required vaccine codes) and the specific timeframes of each data extract will reflect the study inclusion/exclusion criteria described in [Section 9.2](#), the baseline and follow-up periods in [Sections 9.2.4](#) and [9.2.5](#), and the study variables in [Section 9.3](#). All reports and deliverables will contain aggregated results only and will not identify individual patients, physicians, or facilities.

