## 9.7. Data Analysis

### 9.7.1. SCRI

#### 9.7.1.1. Primary Analysis

Descriptive statistics will be used to summarize the baseline characteristics of those who receive the COMIRNATY 2023-2024 Formula. Counts of each safety outcome of interest will be reported within pre-specified risk and control windows. Then, the observed incidence rates of the outcomes of interest will be estimated in the risk window and the control window. Among the individuals who experience an outcome of interest in either the risk window or the control window (but not both), an exact conditional Poisson regression model with the natural logarithm of the person-time as the offset will be used to calculate the relative incidence (rate ratio) and corresponding 95% confidence interval (CI) of the risk period relative to the control period. With the self-controlled design, whereby each individual serves as their own comparator, the analysis accounts for the factors that vary across but not within individuals (i.e., time-invariant covariates).

The results from the SCRI utilizing the Optum pre-adjudicated claims database will be presented in the interim report, while results from the SCRI utilizing the ORD will be presented in the final report.

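### Phase 1 eligibility admits only recipients who have an outcome, which contradicts the planned incidence rates and baseline description for vaccine recipients and leaves the rate denominator unstated

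*Protocol*

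**What the plan says.** Two sets of provisions in the protocol bear on who is in Phase 1.

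**Provisions that admit cases only**
- Section 9.2.1.1 opens with "Patients must meet all of the following inclusion criteria to be eligible for inclusion in Phase 1 of the study". Criterion 4 is "Experience a safety outcome of interest during a risk interval or control period", so a vaccinated person without an event is not eligible.
- The population paragraph of the abstract carries the same condition: "experience a safety outcome of interest during a risk or control period".
- Section 9.6 says that the patients in each data extract "will reflect the study inclusion/exclusion criteria described in" Section 9.2.

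**Provisions that need all recipients**
- The Phase 1 primary objective (8.1.1) is "To estimate the incidence of pre-specified safety events of interest following vaccination with the COMIRNATY 2023-2024 Formula", set against the incidence in a control window.
- Section 9.1.1 monitors the incidence rate "in a general population of individuals who receive the COMIRNATY 2023-2024 Formula", with risk intervals and "control (reference) periods for each vaccinated individual".
- Section 9.7.1.1 first describes the baseline characteristics of vaccine recipients and counts outcomes by window. It then says that "the observed incidence rates of the outcomes of interest will be estimated in the risk window and the control window". Only the next step, the exact conditional Poisson model, is limited to people with an event in one window but not both.

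No section says whose person-time is the denominator of the window-specific rates.

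**The concern.** An incidence rate in vaccine recipients needs the person-time of all eligible recipients. Those without an event supply nearly all of it, and criterion 4 makes them ineligible. An analyst who builds the Phase 1 population from 9.2.1.1 and then computes the rates in 9.7.1.1 divides cases by the time of those same cases. The result carries no information on how common the event is, so the incidence part of the Phase 1 objective is not met. The baseline table would likewise describe cases rather than recipients.

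This matters most for the interim report, which contains only the self-controlled analysis (Table 1) and so has no other incidence estimate to fall back on.

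Section 7 calls the document a combined protocol and SAP, and Annex 1 lists no standalone documents. By the protocol's own account, this is where the population has to be settled.

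**Working it through.** The protocol gives no expected incidence, event count or number of recipients for Phase 1, so there is no stated figure to reproduce. The check asks what the planned rates become under each reading.

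**Inputs from the protocol**
- Window length L is taken from Table 2. Days 1 to 42 give 42 days, days 1 to 28 give 28, days 1 to 21 give 21, and days 0 to 1 (anaphylaxis) give 2.
- The control period equals the risk interval in length (9.3.2.1).

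**Assumptions (not in the protocol)**
- Follow-up is complete in both windows, each case has one event, and the case set is specific to the outcome.
- N is the number of eligible recipients, taken as 100,000 or 1,000,000. The event counts are illustrative.

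**Formulas**, with x1 events in the risk window and x0 in the control window, and 365.25 days per year:
- All-recipient rate, risk window: x1 / (N × L / 365.25).
- Case-only rate, risk window: x1 / ((x1 + x0) × L / 365.25). The control-window rate has x0 in the numerator.
- Sum of the two case-only rates: (x1 + x0) / ((x1 + x0) × L / 365.25) = 365.25 / L per person-year. The event counts and N cancel.
- Rate ratio with equal windows: x1 / x0 under either denominator.

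**Sum of the two case-only rates**

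| L (days) | 365.25 / L, per person-year | Each window if the rate ratio is 1 |
|---|---|---|
| 42 | 8.70 | 4.35 |
| 28 | 13.04 | 6.52 |
| 21 | 17.39 | 8.70 |
| 2 | 182.62 | 91.31 |

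**The two denominators compared, L = 42, rates per 100,000 person-years in each window**

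| N | Events, risk / control | All recipients | Cases only | Ratio, N / (x1 + x0) |
|---|---|---|---|---|
| 1,000,000 | 10 / 10 | 8.70 | 434,821 | 50,000 |
| 1,000,000 | 100 / 100 | 86.96 | 434,821 | 5,000 |
| 100,000 | 10 / 10 | 86.96 | 434,821 | 5,000 |
| 100,000 | 100 / 100 | 869.64 | 434,821 | 500 |

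First row worked through:
- All recipients: 10 / (1,000,000 × 42 / 365.25) = 8.70 per 100,000 person-years.
- Cases only: 10 / (20 × 42 / 365.25) = 4.348 per person-year, or 434,821 per 100,000.

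Across the four rows the all-recipient rate varies 100-fold while the case-only rate does not move.

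**Rate ratio.** With 30 risk-window and 10 control-window events, the ratio is 30 / 10 = 3.00 with either denominator, exact 95% CI 1.43 to 6.88. People without an event contribute nothing to the conditional likelihood, so removing them changes neither the estimate nor its interval.

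**If the case set is not outcome-specific.** Criterion 4 speaks of an outcome without saying which, so a literal Phase 1 set would hold people with any of the 20 listed outcomes. With C such people, all contributing full windows, the two rates for one outcome sum to ((x1 + x0) / C) × 365.25 / L. That is that outcome's share of the case set multiplied by 365.25 / L. The exact 1/L result no longer holds, but the rate still reflects the case mix and window length rather than incidence in recipients.

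**The case against.** The strongest reply is that the protocol nowhere says the rates are divided by case-only person-time, and that its analysis text points the other way. Section 9.1.1 speaks of each vaccinated individual. Section 9.7.1.1 starts from recipients and attaches the case restriction to the regression alone, in narrower terms than criterion 4. This stands: a reader might infer that case-only rates are the planned method, and the text does not support that. What it shows is two incompatible populations and no stated denominator.

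A reader might also infer from 9.6 that recipients without events would never be extracted. That goes too far. The example given there is vaccine codes, and data are extracted once per report. The final report also contains the Phase 2 cohort, whose entry criteria (9.2.2.1) require no outcome, so that extract must hold non-cases. At most the argument touches the interim report.

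Third, conditioning on cases is how a self-controlled risk interval comparison works, and Phase 2 also estimates incidence among matched recipients (9.7.2.2). Both are true. Criterion 4 is sound as a definition of the case set for the model; the problem is its place among the entry criteria. Phase 2 rates come only in the final report and cover follow-up of up to a year, so they do not replace the Phase 1 window rates.

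Finally, it would be wrong to say that Phase 1 admits people who already have the outcome. The qualifying event falls on or after vaccination, and criterion 5 excludes those with the event in the clean period.

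**Conclusion.** The contradiction is real and should be corrected. Section 9.2.1.1 and the abstract define a case-only Phase 1 population; 8.1.1, 9.1.1 and the first part of 9.7.1.1 need all recipients; and the rate denominator is unstated. If criterion 4 governs, the two window rates for an outcome sum to 1/L whatever the true incidence: 8.70 per person-year at 42 days, 13.04 at 28 and 17.39 at 21. This rests on outcome-specific case sets, full follow-up and one event per case. The 500- to 50,000-fold overstatement in the examples also depends on assumed recipient numbers and event counts, and illustrates scale only.

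The point does not reach the Phase 1 comparison. The conditional rate ratio, its confidence interval and the signal rule in 9.3.2 (rate ratio above 3.0 with P below 0.01) are the same under either reading. What is at risk is the absolute incidence rates and the baseline table.

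**What to change.** 1. In 9.2.1.1 and the abstract, either remove criterion 4 from Phase 1 eligibility or state that it defines only the case set for the conditional Poisson model.
2. Define the Phase 1 population as all otherwise eligible COMIRNATY 2023-2024 recipients, with the clean-period exclusion (criterion 5) applied separately for each outcome.
3. In 9.7.1.1, state that the baseline description, outcome counts and incidence rates use all those recipients and their risk- or control-window person-time. Keep the restriction to people with an event in one window but not both for the rate ratio only.

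The cost is a few sentences in the protocol and, for any Phase 1 dataset built from cases alone, retrieval of the remaining recipients. Recipients have to be identified in any event to find the cases. The conditional model needs no change.

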### **9.2.1.2. Exclusion Criteria**

Patients meeting any of the following criteria will not be included in Phase 1 of the study:

1. Are of unknown sex.
2. Have a missing month and year of birth.
3. Have received a COVID-19 vaccine in the 270 days prior to the vaccination date (as defined in Section 9.2.3).
4. Have received a COVID-19 vaccine other than the COMIRNATY 2023-2024 Formula on the same vaccination date (defined in Section 9.2.3).

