### 9.3.2. Outcomes

In both the SCRI and cohort studies, the pre-specified safety outcomes of interest will include the following:

- ADEM
- Anaphylaxis
- Bell's palsy
- CVST
- Convulsions/seizures (non-febrile)
- Encephalomyelitis
- Glomerulonephritis
- Guillain-Barré syndrome
- Herpes zoster
- Immune-mediated myositis
- Immune thrombocytopenia
- Kawasaki disease
- Multi inflammatory syndrome (in children and adults)
- MS
- MI
- Myocarditis/pericarditis
- PE
- Stroke, hemorrhagic
- Stroke, ischemic
- Transverse myelitis

In addition, in Phase 2 of the study, the following pregnancy outcomes will be assessed in pregnant women or their infants, if sample size permits:

- Spontaneous abortion
- Stillbirth
- Preterm birth
- Major congenital malformations
- Small for gestational age

Code lists for the safety outcomes of interest are provided in [Annex 2 \(Appendix III\)](#). Corresponding site of care requirements are listed in Table 2. When possible, outcomes will be defined using a validated claims-based algorithm with high performance ([CBER, 2021](#)).

If a safety signal is detected in the interim report, then medical records will be retrieved for a subset of participants to confirm the presence of that study outcome. A safety signal that requires confirmation through medical record review will be defined as a rate ratio of > 3.0 and a corresponding P value of < 0.01 in the primary analysis of the SCRI design (details in [Section 9.7.1.1](#)). Additionally, medical record review may be conducted for analyses beyond the primary SCRI analysis if a safety signal (defined as a rate ratio of > 3.0 and a corresponding P value of < 0.01) is detected in the interim or final report. Medical records may also be retrieved for AESIs with estimates approaching the pre-specified safety signal threshold.

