### 9.3.3. Covariates

All members of the study cohorts will be described according to covariates identified in the claims data. Demographic attributes will be determined on the vaccination/cohort entry date, while other factors will be assessed in the one year prior to the cohort entry date. Unless specified as for descriptive purposes only, the covariates listed will be included in the PS models. All variables are binary unless otherwise specified.

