$$\begin{aligned} & \text{logit}\{P(T_i = 1 \mid \mathbf{X}_i)\} \\ &= \beta_0 + \beta_1 \text{Sex (binary)}_i + \beta_2 \text{Age (categorical)}_i \\ &+ \beta_3 \text{Calendar month (categorical)}_i + \beta_4 \text{Geographic region (categorical)}_i \\ &+ \beta_5 \text{Asthma (binary)}_i + \beta_6 \text{Non-malignant blood disorders (binary)}_i \\ &+ \beta_7 \text{Chronic lung disease (binary)}_i + \beta_8 \text{Down syndrome (binary)}_i \\ &+ \beta_9 \text{Heart disease (binary)}_i \\ &+ \beta_{10} \text{History of SARS-CoV-2 infection (binary)}_i \\ &+ \beta_{11} \text{Immunocompromised status (binary)}_i \\ &+ \beta_{12} \text{Kidney disorders (binary)}_i + \beta_{13} \text{Liver disorders (binary)}_i \\ &+ \beta_{14} \text{Neurological or neurodevelopmental conditions (binary)}_i \\ &+ \beta_{15} \text{Malignant neoplasms (binary)}_i + \beta_{16} \text{Obesity (binary)}_i \\ &+ \beta_{17} \text{Type II diabetes (binary)}_i \\ &+ \beta_{18} \text{Number of hospitalizations in prior year (continuous)}_i \\ &+ \beta_{19} \text{Number of emergency room visits in prior year (continuous)}_i \\ &+ \beta_{20} \text{Number of outpatient encounters in prior year (continuous)}_i \\ &+ \beta_{21} \text{Seasonal influenza vaccination (binary)}_i \\ &+ \beta_{22} \text{RSV vaccination (binary)}_i + \beta_{23} \text{Systemic immunomodulators (binary)}_i \\ &+ \beta_{24} \text{Oral corticosteroids (binary)}_i + \beta_{25} \text{Antivirals (binary)}_i \\ &+ \beta_{26} \text{Antibiotics (binary)}_i + \beta_{27} \text{Identified empiric variables (binary)}_i, \end{aligned}$$

where  $T_i$  denotes exposure status for individual  $i$ , with  $T_i = 1$  indicating a recorded vaccination of the COMIRNATY 2023-2024 Formula and  $T_i = 0$  indicating no recorded vaccination of the COMIRNATY 2023-2024 Formula.

A greedy digit-based matching algorithm will be used, in which patients exposed to the COMIRNATY 2023-2024 Formula are matched without replacement to comparator patients at a given level of precision defined by the number of digits of the PS (Parsons, 2001), to a maximum of 8 decimal places. When no further matches are available at a given level of precision, the number of digits is sequentially reduced until a maximum allowable caliper of 0.1 is reached, thereby ensuring that the matched cohorts are comparable with respect to the underlying measured risk factors. Matching by propensity score will be conducted within

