#### 9.7.2.4. Subgroup Analysis

If sample size permits, the main analysis will be restricted to the following subgroups:

- Individuals with concomitant administration of a non-COVID-19 vaccine (e.g., seasonal influenza, RSV) on cohort entry date; specific analyses will be performed among individuals receiving seasonal influenza vaccine and those receiving RSV vaccine
- Immunocompromised individuals
- Individuals with specific baseline comorbidities, such as a chronic lung, heart, kidney or liver condition; cancer; Down syndrome or other neurological or neurodevelopmental disorders; and blood disorders
- Individuals with prior SARS-CoV-2 infection
- Individuals with prior COVID-19 vaccination
- Pregnant women
- Individuals aged < 18 years
- Individuals aged  $\geq$  65 years

For the subgroup analysis, the propensity score will be included in the model as a covariate, given that some matched strata may be broken by restricting both the COMIRNATY 2023-2024 Formula cohort and the comparator cohort by the above attributes. As with the primary analysis, unconditional Poisson regression will be used, and the model will account for individuals who are included in both groups.

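### The SCRI cannot separate COMIRNATY from a non-COVID-19 vaccine given on the same day, and Phase 2 does not check Day 0 co-vaccination for balance

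*Protocol*

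**What the plan says.** **Phase 1.** Section 9.2.1.2 excludes people who "Have received a COVID-19 vaccine other than the COMIRNATY 2023-2024 Formula on the same vaccination date". It has no exclusion for a same-day influenza, RSV or other non-COVID-19 vaccine. On confounding, 9.7.1.1 says that "the analysis accounts for the factors that vary across but not within individuals". It sets out no stratum, covariate or sensitivity analysis for a co-administered product. The signal rule in 9.3.2 rests on this estimate: "a rate ratio of > 3.0 and a corresponding P value of < 0.01 in the primary analysis of the SCRI design".

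**Phase 2.** The propensity score equation in 9.7.2.1 has binary terms for seasonal influenza and for RSV vaccination. Section 9.3.3 takes demographics on the entry date, while "other factors will be assessed in the one year prior to the cohort entry date". Under 9.3.1.2 a comparator may qualify through a vaccine other than COMIRNATY, so the comparator's own entry event can be an influenza or RSV vaccination. Section 9.7.2.3 repeats the comparison against three comparator subsets: another 2023-2024 COVID-19 vaccine, a non-COVID-19 vaccine, or no vaccine at entry. Section 9.7.2.4 adds, if sample size permits, a subgroup of "Individuals with concomitant administration of a non-COVID-19 vaccine (e.g., seasonal influenza, RSV) on cohort entry date", with separate influenza and RSV analyses.

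Section 9.9 does not list same-day co-administration as a limitation of either design.

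**The concern.** A co-vaccine given on Day 0 is an exposure that changes within a person, and it changes at the same moment as the COMIRNATY exposure. The risk interval of one is the risk interval of the other. A design that removes only time-fixed factors cannot separate them. The protocol treats a second COVID-19 vaccine on Day 0 as reason enough to exclude, and it names co-administration first among its Phase 2 subgroups. It therefore expects the situation but leaves it unhandled in Phase 1.

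What is at stake is attribution. Under Table 1 the interim report contains only the SCRI, and the milestone notes say that report is meant to inform decisions on the next adapted vaccine. The record review in 9.3.2 is there to confirm that the outcome occurred; it does not settle which vaccine preceded it. Some outcome codes in Appendix III are vaccine-related but not product-specific, for example T80.52XA (anaphylaxis) and G04.02 (encephalomyelitis).

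In Phase 2 the question is narrower: whether Day 0 co-vaccination is balanced between the arms, and whether anyone would see it if it were not.

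**Working it through.** The protocol states no co-administration share, no co-vaccine effect and no sample size, so there is no figure to reproduce. What follows is bias algebra with assumed inputs. The true COMIRNATY rate ratio is set to 1.

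**SCRI.** Let p be the share co-vaccinated on Day 0 and RRc the co-vaccine's rate ratio in the risk interval. Assume equal background rates with and without a co-vaccine, and no co-vaccine effect left in the control period.

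Apparent rate ratio = (1 − p) × 1 + p × RRc = 1 + p(RRc − 1)

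| p (assumed) | RRc = 2 | RRc = 3 |
|---|---|---|
| 20% | 1 + 0.2 × 1 = 1.2 | 1 + 0.2 × 2 = 1.4 |
| 40% | 1.4 | 1.8 |
| 60% | 1.6 | 2.2 |

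For co-administration alone to push the estimate above 3.0, p must exceed 2/(RRc − 1). That is 0.67 at RRc = 4, 0.50 at RRc = 5 and 0.33 at RRc = 7. At RRc = 3 the limit is 1.0, so it cannot happen. At RRc = 1 there is no bias.

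**Cohort.** Let c1 and c0 be the Day 0 shares in the exposed and comparator arms, and r the co-vaccine's rate ratio.

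Within the risk interval: (1 + c1(r − 1)) / (1 + c0(r − 1))

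Over a full year, with an interval of w days: replace (r − 1) by (r − 1)w/365

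With r = 3 and w = 42 (the longest interval in Table 2):

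| c1 / c0 (assumed) | Within interval | Over 365 days |
|---|---|---|
| 50% / 0% | 2.0/1.0 = 2.00 | 1.12 |
| 50% / 10% | 2.0/1.2 = 1.67 | 1.09 |
| 50% / 30% | 2.0/1.6 = 1.25 | 1.04 |
| 50% / 50% | 1.00 | 1.00 |
| 30% / 50% | 1.6/2.0 = 0.80 | 0.96 |

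The 1.12 is 1 + 0.5 × 2 × 42/365. With a 21-day interval the same row gives 1 + 0.5 × 2 × 21/365 = 1.06. Follow-up shorter than a year dilutes less.

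**The planned Phase 2 splits.** Section 9.7.2.3 subsets comparators only; the exposed arm stays mixed. Keep c1 = 50% and r = 3, and assume the comparators' non-COVID-19 vaccine has the same effect. The vaccinated-comparator subset sets c0 = 1 and a null effect reads 2.0/3.0 = 0.67 within the interval. The no-vaccine subset sets c0 = 0 and it reads 2.00. The two comparisons err in opposite directions, and neither isolates COMIRNATY. The 9.7.2.4 subgroup does align both arms, but only for the co-vaccinated.

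**The case against.** The strongest objection concerns Phase 2. A reader might infer that both primary analyses assign co-vaccine effects to COMIRNATY, or that the propensity score ignores influenza and RSV vaccination. The documents support neither. The score has both terms. Comparators can be vaccinated on Day 0 too, so only the between-arm difference carries over, and it can be zero or reversed. The comparator splits in 9.7.2.3 carry no sample-size condition and give some view of the mix. Section 9.2.4 also allows other assessment windows for specific covariates. What remains is that no other window is fixed for these two terms. As worded, a Day 0 dose is in neither the score nor the standardized differences, which 9.7.2.1 computes for covariates in the model.

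A reader might also infer that co-administration would by itself trigger the signal rule. Over the range in the first table it would not: every value is below 3.0. Nor does the protocol say which outcomes influenza or RSV vaccines can cause, so the size of any bias is unknown.

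Finally, it could be said that this belongs in a separate analysis plan. Section 7 calls this document the combined protocol and statistical analysis plan, and Annex 1 lists no standalone documents.

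**Conclusion.** The SCRI part holds. A same-day non-COVID-19 vaccine is neither excluded, stratified nor tested in Phase 1, and any effect it has in the risk interval enters the COMIRNATY rate ratio. With RRc above 1, a null COMIRNATY effect reads above 1: 1.2 to 2.2 for assumed p of 20–60% and RRc of 2–3. Those inputs are illustrations, not estimates, and the results stay below the signal threshold. The harm is that an elevated estimate could not be attributed, and that the planned analyses could not show whether a co-vaccine contributed.

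The Phase 2 part holds only as an unchecked imbalance. Its direction is not fixed, and over a full year it is small in the examples (0.96 to 1.12 at r = 3 with a 42-day interval). Neither phase plans an estimate for COMIRNATY given without a same-day non-COVID-19 vaccine. This is an inexpensive improvement to interpretability, not a flaw that invalidates either design.

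**What to change.** 1. In 9.7.1.1, add SCRI rate ratios for doses with and without a same-day non-COVID-19 vaccine, using the Appendix II codes. Read any signal also in the COMIRNATY-alone stratum. The planned interim report date (30 June 2024) precedes this version, so this applies to the final-report SCRI. The cost is lower precision in each stratum.
2. In 9.7.2.4, add a subgroup with no same-day non-COVID-19 vaccine, applied to both cohorts, as the counterpart of the existing concomitant-vaccine subgroup. It uses the matched master cohort and the subgroup model already planned.
3. Report the Day 0 influenza and RSV vaccination shares by arm in the matched cohort. If they are imbalanced, add separate Day 0 indicators to the outcome model; 9.7.2.2 already provides for imbalanced covariates there. Do not widen the prior-year covariate to include Day 0. A comparator vaccinated months earlier would then count the same as a person co-vaccinated on Day 0, and same-day exposure would stay unbalanced.
4. Name same-day co-administration as a limitation in 9.9.

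None of this requires re-matching. That matters because one master cohort serves all Phase 2 analyses, and the final report is planned for 30 April 2026, six weeks after this version (18 March 2026).
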